### 14.2 Power Analysis:

Percent change in BMI from baseline (randomization) and 6 months will serve as the primary outcome for which the sample size determination is based. Sample size was based on feasibility. We consider variability estimates from our previous experience with anti-obesity medication trials in the adolescent population, suggesting a standard deviation of approximately 8.9 and a conservative correlation between baseline and follow-up of 0.75. Based on an overall sample size of 30 (15 in each of two treatment arms) and type I error of 0.05, we will have 80% power to detect treatment difference of 6%. This percent change in BMI is clinically significant and similar to other results found in the previous PHN/TPM trials. We also appreciate degree of attrition may be unavoidable. In the event of 10% attrition (recent experience for our study group in a trial involving a similar adolescent population with severe obesity), we will have 80% power for a treatment difference of 6.3%.

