monotherapy and 47% on metformin and intensive lifestyle therapies progressed to exogenous insulin dependence within four years. Furthermore, the Restoring Insulin Secretion (RISE) Pediatric Medication Study demonstrated that metformin ± insulin did not slow the progression of β-cell deterioration in adolescents with T2D or impaired glucose tolerance. Making matters worse, insulin-associated weight gain can increase BMI and body fat, and exacerbate insulin resistance, requiring the use of additional insulin therapy. Conversely, tight glycemic control is imperative as adolescents with T2D are also more likely to have diabetes-related comorbidities such as hypertension, atherosclerosis, and kidney disease (albuminuria) earlier compared to adults.

Even the two-newly FDA-approved glucagon-like peptide receptor agonists (GLP-1RAs) for youth ≥ 10 years with T2DM (liraglutide 1.8 mg and exenatide ER) did not result in the weight reduction recommended for pediatric patients by the ADA. For example, liraglutide at doses up to 1.8 mg/day did not significantly reduce BMI in 134 adolescents, aged 10-17 years with T2DM and overweight/obesity (mean BMI of 33.90 + 9.25 kg/m^2) after a 26-week double-blind randomized, control trial (RCT). At the end of the 26-week open-label extension of this trial, a minimal estimated treatment difference in BMI of -0.89 kg/m^2 or a 2.73% decrease between liraglutide and placebo groups was found. Although the BMI reduction with liraglutide 1.8mg/day is statistically significant, it remains unclear the clinical significance of this finding. Exenatide ER also did not significantly reduce weight compared to placebo after a 24-week randomized controlled trial (-0.59 + 0.665 kg vs + 0.63 + 0.882. kg, respectively, p=0.307) and the 28 open-label extension (0.04+ 6.09 kg versus -0.04 + 4.69 kg, respectively) of 84 In the randomized control trial of adolescents with obesity (mean BMI: 36.36 +8.57 kg/m^2) and T2DM, previously treated with diet and exercise alone or with metformin + a sulfonylurea and/or insulin.

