**Table 2. Adverse Events of Phentermine/Topiramate Treatment in Adolescents with Obesity**

Adverse Event Description	Placebo Group (%)	Phentermine/Topiramate Group (%)
Dry Mouth	0%	8%
Abdominal Pain	0%	0%
Constipation	0%	0%
Diarrhea	0%	0%
Ear Infection	0%	0%
Nasopharyngitis	7%	0%
Pharyngitis	0%	0%
Procedural Pain	7.1%	0%
Urine Osmolarity Increase	0%	0%
Back Pain	0%	0%
Headache	21%	15%
Paresthesia	7%	31%
Dizziness	7%	0%
Insomnia	7%	0%
Oropharyngeal Pain	7%	0%

At 56 days, the percent change in body weight was +1.1±2.8% in the placebo group and -5.0±3.4% in the PHN/TPM group (placebo-subtracted weight loss of 6.1%). Owing to the relatively small sample size and the fact that weight reduction was a secondary outcome variable, the manufacturer did not perform a statistical analysis on these results. However, the preliminary results further support our estimated treatment effect, particularly considering the treatment period was only two months (56 days). Indeed, the degree of placebo-subtracted

weight loss was slightly better than what was observed in the adult trials at the two-month time-point, suggesting that the effects are at least additive when these two medications are used together.

In summary, this portfolio of preliminary work: 1) demonstrates our Center's leadership role in, and commitment to, the field of pediatric obesity medicine; 2) highlights the benefits (weight loss and cardiometabolic risk factor improvement) as well as our experience with this intervention; 3) provides preliminary evidence supporting the safety, efficacy, and acceptability of combination therapy in adolescents with severe obesity; and 4) sets the stage for taking this next important step.

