### 14.3 Statistical Analysis:

Descriptive analyses of baseline characteristics and outcomes will include means and standard deviations, median and range for continuous variables and frequencies for categorical variables. Treatment adherence will also be evaluated by the methods described above. Safety analyses will be primarily descriptive reporting the number and percentage of adverse events. All safety outcomes will be evaluated and monitored throughout the trial. Confidence intervals (CIs) and p-values will be based on robust variance estimation. Statistical significance will be considered as  $p < 0.05$ .

Aim 1: The primary analysis will be conducted using the ITT population to compare the mean BMI percent change (primary outcome measure) from randomization to 6 months of follow-up between the groups, adjusted for BMI at randomization for added precision. We hypothesize that with participants treated with PHN/TPM will demonstrate greater BMI percent change compared to controls at 6 months. Supportive analyses using the PP population will also be conducted along with consideration of adjustment for residual imbalances

between treatment groups after randomization (e.g., in sex as a biological variable). Longitudinal analyses will also be conducted, incorporating the multiple time points through the open-label extension (6 months to 12 months follow-up) during which these BMI measurements will be obtained. This will examine durability of changes observed over the masked portion of follow-up, as well as provide additional safety information. Supportive analyses using the PP population will also be conducted.

Aim 2: Secondary outcomes will be analyzed in the same fashion as the primary endpoint wherein analyses will be adjusted for values at randomization. Outcome measures for Aim 2 are c-peptide index ( $\Delta C_{30}/\Delta G_{30}$ ), insulin sensitivity (1/fasting insulin),  $\beta$ -cell function relative to insulin sensitivity (oral disposition index [oDI]), A1c (%), and total daily insulin dose (units/kg/day). We hypothesize that participants treated with PHN/TPM will demonstrate improved insulin sensitivity and  $\beta$ -cell function compared to those assigned to placebo as measured by OGTT, A1c and total daily insulin doses. Complementary secondary analyses will also be conducted for each secondary outcome as described for the primary outcome.

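### The 80% power for a 6% difference in percent BMI change rests on an SD of 8.9 with no stated variable or unit, reduced by a correlation that belongs to a different outcome

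*Combined protocol and SAP*

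**What the plan says.** Section 14.2 names the outcome used for sizing: "Percent change in BMI from baseline (randomization) and 6 months will serve as the primary outcome". It says "Sample size was based on feasibility" and takes its variability from the group's earlier adolescent trials, "suggesting a standard deviation of approximately 8.9 and a conservative correlation between baseline and follow-up of 0.75". No variable, unit or dataset is attached to 8.9.

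With 15 per arm and a type I error of 0.05 (sidedness not stated), it concludes "we will have 80% power to detect treatment difference of 6" percent. With 10% attrition it concludes "we will have 80% power for a treatment difference of 6.3" percent. It describes the 6% effect as clinically significant.

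Section 14.3, Aim 1, gives the primary analysis: "compare the mean BMI percent change (primary outcome measure) from randomization to 6 months of follow-up between the groups, adjusted for BMI at randomization".

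**The concern.** Adjusting for a covariate multiplies the outcome SD by sqrt(1 − r²), where r is the correlation between the analysed outcome and that covariate. The outcome here is percent change and the covariate is baseline BMI. A correlation between baseline and follow-up describes BMI measured twice. It is the right r when follow-up BMI is the outcome, and the answer then comes out in the units of the BMI SD. It is not the r for percent change, and the plan does not give that one.

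At stake is the plan's only statement of what the trial can detect. Readers will use it to interpret a null result, and later trials may be planned from it.

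**Working it through.** **Inputs.** From section 14.2: SD 8.9, correlation 0.75, 15 per arm, 10% attrition (27 in total, 13.5 per arm), alpha 0.05 and power 80%. A two-sided test is inferred because it reproduces the figures. From sections 2.1 and 2.2: baseline BMI of 33.90 (SD 9.25), 36.36 (8.57), 37.8 (7.1) and 43.2 (10.2) kg/m². From section 2.2, under Table 2: percent-change SDs of 2.8 (n = 14) and 3.4 (n = 13), for body weight at 56 days.

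**1. Reproduce the plan.** Detectable difference = (1.96 + 0.84) × residual SD × sqrt(2/n).
- Residual SD = 8.9 × sqrt(1 − 0.75²) = 8.9 × 0.6614 = 5.887.
- n = 15: 2.8016 × 5.887 × sqrt(2/15) = 6.02. Power for 6% is 79.7%.
- n = 13.5: 2.8016 × 5.887 × sqrt(2/13.5) = 6.35. Power for 6.3% is 79.4%.

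The other two-sided normal variants do not fit at 15 per arm. A change-score SD, 8.9 × sqrt(2 × 0.25) = 6.29, gives 6.44. The undiscounted 8.9 gives 9.10.

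**2. General multiplier.** For a residual SD of percent change s, the detectable difference at 15 per arm is 2.8016 × sqrt(2/15) × s = 1.02 s (normal) or 1.06 s (noncentral t). At 13.5 per arm it is 1.08 s or 1.12 s.

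**3. Reading (a): 8.9 is the SD of percent change, in points.**
- Unadjusted: 9.1% (normal) or 9.4% (t). With attrition: 9.6% or 10.0%. Power for 6% is 45% (normal) or 43% (t).
- Adjusted: treat percent change as change divided by mean BMI M, and let D = 8.9 × M/100 be the SD of change in kg/m². The correlation of baseline BMI with change is (S₁² − S₀² − D²)/(2 S₀ D), where S₀ and S₁ are the baseline and follow-up BMI SDs. The document gives no S₁.
- With S₁ = S₀, the four BMI pairs above give correlations of −0.16 to −0.24.
- With S₁ within 10% of S₀, they give about −0.45 to +0.16. For example, at 33.90 (9.25) with S₁ = 0.9 S₀: D = 3.017, and (−0.19 × 85.56 − 9.10)/(2 × 9.25 × 3.017) = −0.45.
- Over that range, the detectable difference by t is about 8.4% (9.44 × sqrt(1 − 0.454²) = 8.41) to 9.4%.

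**4. Reading (b): 8.9 is the SD of BMI, in kg/m².** The result is 6.02 kg/m². As a share of mean BMI, that is 6.02/43.2 = 13.9% to 6.02/33.9 = 17.8%. To reach 6% under this reading, the baseline/follow-up correlation would have to be about 0.96 to 0.98, not 0.75.

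**5. A favourable bound.** Pooled 56-day SD = sqrt((13 × 2.8² + 12 × 3.4²)/25) = 3.10. The detectable difference is 1.023 × 3.10 = 3.17% (normal), or 3.29% by t.

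**6. Residual SD that would support the claim.** Normal: 6/1.023 = 5.87 points for 6%, and 6.3/1.078 = 5.84 for 6.3%. By t: 6/1.061 = 5.65 and 6.3/1.124 = 5.61.

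**The case against.** Nothing is miscalculated: given its inputs, the plan's arithmetic is right. That stands, and the point is an unsupported power input rather than an arithmetic slip. The discount formula is also not written in the plan. It is inferred because it reproduces both figures.

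The sample size is openly based on feasibility in a pilot, so no design decision rests on the power figure. That also stands. But feasibility justifies 30 participants; it does not support a separate, unqualified claim of 80% power.

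The paragraph opens by naming percent change, so 8.9 may be meant as its SD. That is a fair reading, but it is reading (a), where a baseline/follow-up correlation does not justify the discount. Nor can 0.75 readily stand in for the correlation of baseline BMI with percent change: with a BMI SD of 8.9 at both times and r = 0.75, simulation puts that correlation at only about −0.27 to −0.33.

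A reader might infer that the trial is underpowered, or that it needs the roughly 35 per arm that an undiscounted 8.9 would require for 6%. The document does not support either. What 8.9 measures is unknown. It lies within the quoted BMI SDs of 7.1 to 10.2 kg/m² (for example "mean BMI of 33.90 + 9.25 kg/m"²) and is nearly three times the only percent-change SDs shown: "the percent change in body weight was +1.1±2.8% in the placebo group and -5.0±3.4% in the PHN/TPM group". The plan also calls 0.75 conservative. Those smaller SDs are weak evidence in turn, since they describe body weight at 56 days and not BMI at 6 months.

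**Conclusion.** The point holds as a defect in the inputs. Under neither natural reading of 8.9 do the stated inputs yield 80% power for a 6% difference in percent BMI change. No other section supplies the missing SD or correlation.

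The size depends on what 8.9 is. As percentage points, the detectable difference is about 9% unadjusted. Baseline adjustment brings it to roughly 8.4% to 9.4% by t, provided the follow-up BMI SD is within 10% of the baseline SD, which is an assumption. As kg/m², it is about 6 kg/m². If the 6-month SD were as small as the 56-day weight SD, it would be near 3.2%.

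The direction of the error is therefore open. Confidence is high that the claim is unsupported as written, and low for any single replacement figure.

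**What to change.** In section 14.2 only:

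1. State what 8.9 measures and in what unit.
2. Base the calculation on the SD of 6-month percent BMI change and its correlation with baseline BMI, both from the group's earlier trials, in place of the 0.75.
3. Restate the detectable difference with and without attrition. Keep 6% (6.3%) only if the residual SD is at most about 5.9 (5.8) percentage points by normal approximation, or 5.65 (5.6) by t.
4. If no such estimate exists, replace the 80% power claim with the detectable difference over a range of SDs, using the multipliers above.

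The cost is a one-paragraph edit, with no change to sample size, endpoint or analysis. The downside is that the stated detectable difference may become less favourable.

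### Section 14.2's 80% power at a 6% difference matches a large-sample formula; on the same inputs a 15-per-arm baseline-adjusted test that holds 5% type I error has about 75%

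*Combined protocol and SAP*

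**What the plan says.** Section 14.2 sets the sample size by feasibility: 30 participants, 15 per arm, type I error 0.05. Its variability inputs come from the group's earlier trials, "suggesting a standard deviation of approximately 8.9" together with "a conservative correlation between baseline and follow-up of 0.75". From these it states that "we will have 80% power to detect treatment difference of 6" percent and, if 10% are lost, "we will have 80% power for a treatment difference of 6.3" percent. It gives no formula, sidedness or reference distribution.

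Section 14.3 (Aim 1) compares mean BMI percent change at 6 months between arms in the ITT population, "adjusted for BMI at randomization for added precision". It bases confidence intervals and p-values on a robust variance, without naming the variant or the reference distribution. "Statistical significance will be considered as" p below 0.05, again with no sidedness. For participants without a final measurement, section 14.4 carries the last observation forward in the primary analysis.

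**The concern.** The normal-quantile formula treats the residual variance and the baseline slope as known. Here both must be estimated from 30 people, which leaves 27 residual degrees of freedom. A test that keeps its type I error at 0.05 therefore needs a larger critical value, and it pays a little more for chance baseline imbalance between arms. If the stated 80% ignores this, it is too high on the plan's own inputs: the chance of missing a true 6% difference is nearer 25% than 20%. Section 14.2 calls that difference clinically significant, so readers will rely on the power quoted for it.

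**Working it through.** **Inputs (section 14.2):** SD 8.9, correlation 0.75, 15 per arm, type I error 0.05, 10% attrition (27 participants, 13.5 per arm). **Assumptions:** two-sided test; SD and correlation both apply on the percent-change scale.

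**1. Reproducing the stated figures.**
- Residual SD after baseline adjustment: 8.9 × √(1 − 0.75²) = 8.9 × √0.4375 = 5.887.
- Standard error, 15 per arm: 5.887 × √(2/15) = 2.150. Difference for 80% power: (1.960 + 0.842) × 2.150 = 6.02. Power at 6%: 79.7%.
- Standard error, 13.5 per arm: 5.887 × √(2/13.5) = 2.266. Difference for 80% power: 2.802 × 2.266 = 6.35. Power at 6.3%: 79.4%.

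These match 6% and 6.3%. The other variants tried do not give the pair:

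| Variant | 15 per arm | 13.5 per arm |
|---|---|---|
| Change-score SD, 8.9 × √(2 × 0.25) = 6.293 | 6.44 | 6.79 |
| Unadjusted SD 8.9 | 9.10 | 9.60 |
| One-sided, baseline-adjusted, normal | 5.35 | 5.63 |
| Two-sided, baseline-adjusted, noncentral t | 6.25 | 6.62 |

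**2. Using t quantiles.** With 27 degrees of freedom the critical value is 2.052 instead of 1.960. The noncentrality at 6% is 6 / 2.150 = 2.79. Noncentral t power is 76.8%, and the 80%-power difference is 6.25%.

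**3. Also estimating the baseline slope.** Chance baseline imbalance inflates the variance of the treatment effect by about 1 + 1/(N − 4) = 1 + 1/26 = 1.038 for N = 30. Power at 6% falls to 75.2%, and the 80%-power difference becomes 6.37%. Simulating the baseline-adjusted regression with 200,000 trials also gives 75.2% at 6%, and 80.0% at 6.37%.

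**4. Using a robust variance, as section 14.3 plans.** Simulation with 40,000 trials per setting, 15 per arm:

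| Variance and reference | Power at 6% | Type I error |
|---|---|---|
| Model-based, t | 75.3% | 4.8% |
| HC1, t | 75.4% | 4.9% |
| HC2, t | 75.3% | 4.9% |
| HC3, t | 71.7% | 3.8% |
| HC3, normal | 74.6% | 4.7% |
| HC1, normal | 78.0% | 6.0% |
| HC0 (uncorrected), normal | 81.0% | 7.3% |

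Repeat runs put the HC0 error at about 7.5%. No variant tried both reaches 80% power and holds 0.05.

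**5. With 27 participants analysed.** At 6.3%, noncentral t (24 degrees of freedom) gives 76.0%. Simulated baseline-adjusted analyses give 74.3% (14 and 13), 73.0% (13 per arm) and 75.6% (14 per arm). The 80%-power difference is 6.62% by t, or 6.76% with variance inflation 1 + 1/23.

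**The case against.** Several objections have force.

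- **The formula is inferred.** Section 14.2 names none. The match on both figures is close, but it remains a match between rounded numbers.
- **The test is not fully specified.** Section 14.3 calls for robust variance and leaves the rest open. A reader might infer that the planned test must use t quantiles, or that 75% is exactly its power. The documents support neither: power at 6% runs from 71.7% to 81.0% across the variants. What stands is that those at 78% and above exceed the stated type I error.
- **A one-sided test would exceed the claim.** It would have about 86% power at 6% (noncentral t, 27 degrees of freedom). But the one-sided calculation does not reproduce the stated differences, and section 14.4 refers to 95% intervals.
- **Attrition is not complete-case in the primary analysis.** Last observation carried forward keeps dropouts in, so 27 participants with 24 degrees of freedom is the power section's scenario, not the planned primary analysis. This stands, and it limits the 6.8% figure. The 15-per-arm result does not depend on it.
- **The inputs are softer than the correction.** The SD is approximate, the correlation is called conservative, and the scale of both is unstated. Under step 3, 80% power at 6% returns with a correlation of about 0.78 or an SD of about 8.4, and an unadjusted SD of 8.9 would move the detectable difference to 9.10%. So the input question can matter more than this one. Even so, section 14.2 quotes 80% at 0.75 and 8.9.
- **This is a pilot sized by feasibility.** No decision on sample size or conduct turns on these points of power.

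**Conclusion.** The stated 80% is not delivered on the plan's own inputs by any test tried that holds type I error at 0.05. Power at 6% with 15 per arm is about 75%: 76.8% from the t correction alone, about 75% with the slope estimated or with HC1 or HC2 and t, and about 72 to 75% with HC3. The shortfall is 80 − 76.8 = 3.2 to 80 − 75.2 = 4.8 points for the t-based calculations. Equivalently, the 80%-power difference is 6.25 to 6.37% rather than 6%.

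This rests on a two-sided test and on reading the SD and correlation on the percent scale, which section 14.2 does not confirm. A reader might infer that the trial is too small or its design unsound. The documents do not support that: the sample size was set by feasibility, the gap is modest, and only the stated figures need correcting.

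**What to change.** Keep 30 participants and make these wording changes:

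- In section 14.3, name the small-sample form of the robust variance and its reference distribution (for example HC2 with t quantiles), and say that the test is two-sided.
- In section 14.2, name the method and restate the result for that test: on the present inputs and HC2 with t, about 75% power for a 6% difference, or 80% power for about 6.4%. If HC3 with t is chosen instead, power at 6% is about 72%, and the 80%-power difference must be recomputed.
- Replace the attrition sentence with about 6.8% for 80% power if only 27 participants are analysed. Label it a complete-case scenario, because the primary analysis carries the last observation forward.
- State the scale of the SD and the correlation, and redo all figures the same way if either is revised.

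The cost is a few sentences and slightly less favourable figures. Sample size, visits and data collection stay as they are.

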### 14.3 Statistical Analysis:

Descriptive analyses of baseline characteristics and outcomes will include means and standard deviations, median and range for continuous variables and frequencies for categorical variables. Treatment adherence will also be evaluated by the methods described above. Safety analyses will be primarily descriptive reporting the number and percentage of adverse events. All safety outcomes will be evaluated and monitored throughout the trial. Confidence intervals (CIs) and p-values will be based on robust variance estimation. Statistical significance will be considered as  $p < 0.05$ .

Aim 1: The primary analysis will be conducted using the ITT population to compare the mean BMI percent change (primary outcome measure) from randomization to 6 months of follow-up between the groups, adjusted for BMI at randomization for added precision. We hypothesize that with participants treated with PHN/TPM will demonstrate greater BMI percent change compared to controls at 6 months. Supportive analyses using the PP population will also be conducted along with consideration of adjustment for residual imbalances

between treatment groups after randomization (e.g., in sex as a biological variable). Longitudinal analyses will also be conducted, incorporating the multiple time points through the open-label extension (6 months to 12 months follow-up) during which these BMI measurements will be obtained. This will examine durability of changes observed over the masked portion of follow-up, as well as provide additional safety information. Supportive analyses using the PP population will also be conducted.

Aim 2: Secondary outcomes will be analyzed in the same fashion as the primary endpoint wherein analyses will be adjusted for values at randomization. Outcome measures for Aim 2 are c-peptide index ( $\Delta C_{30}/\Delta G_{30}$ ), insulin sensitivity (1/fasting insulin),  $\beta$ -cell function relative to insulin sensitivity (oral disposition index [oDI]), A1c (%), and total daily insulin dose (units/kg/day). We hypothesize that participants treated with PHN/TPM will demonstrate improved insulin sensitivity and  $\beta$ -cell function compared to those assigned to placebo as measured by OGTT, A1c and total daily insulin doses. Complementary secondary analyses will also be conducted for each secondary outcome as described for the primary outcome.

Exploratory Aim: In an exploratory fashion, we will compare the mean change in total body- and visceral fat (expressed as percent and absolute) and cardiometabolic measures from randomization to 6 months of follow-up between the groups, adjusted for randomization values for added precision.

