#### 14.4 Data Integrity:

Despite efforts, it is possible that some data will be missing, which could limit the interpretation and generalizability of results. If the data are missing at random, conditioned on measured covariates, then supplementary analyses adjusting for these covariates will produce unbiased results. For potential missing data mechanisms beyond measured covariates, we will examine the extent to which results may be affected. Imputation techniques will be considered for missing data issues (e.g., multiple imputation). In particular, for the primary analysis we will use a last observation carried forward approach for participants on whom we do not have a final measurement. Additional complementary analyses will incorporate Markov Chain Monte Carlo (MCMC) multiple imputation to handle missing data. The imputation model will be stratified by treatment group and include baseline values at randomization. Additional variables for possible inclusion in the model include age, race, sex, and Tanner stage, though unlikely to be more than one in any single model due to sample size limitations. MCMC imputation will be used to estimate treatment group differences, 95% confidence intervals and P values; observed data will be used to estimate within treatment group changes. If the analyses with and without multiple imputed values differ

substantially, then exploratory analyses will be performed to evaluate factors that may have contributed to the differences. Secondary endpoints will be handled similarly.

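### Robust variance is planned without a small-sample form or reference distribution, so with 15 per arm the 0.05 level in section 14.2 is met only under some readings

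*Combined protocol and SAP*

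**What the plan says.** Section 14.3 sets the basis of inference for the whole trial in two sentences: "Confidence intervals (CIs) and p-values will be based on robust variance estimation", and "Statistical significance will be considered as" p < 0.05. The primary analysis compares mean percent change in BMI at 6 months between the randomized groups, "adjusted for BMI at randomization for added precision". Secondary outcomes are to be analysed in the same way, each adjusted for its value at randomization.

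Section 14.2 gives the size and level: "Based on an overall sample size of 30 (15 in each of two treatment arms) and type I error of 0.05". It adds that "we will have 80% power to detect treatment difference of 6" percent, with inputs described as "suggesting a standard deviation of approximately 8.9 and a conservative correlation between baseline and follow-up of 0.75".

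Neither section says which robust estimator is meant, whether it carries a small-sample correction, or whether limits and p-values use normal or t quantiles. Section 14.4 recognizes the small sample only when it limits the covariates in the imputation model.

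**The concern.** Robust (sandwich) variance is justified in large samples. In a small regression the fitted residuals are on average smaller than the true errors, so the uncorrected estimator is biased low. Normal quantiles then narrow the interval further, because they ignore the uncertainty in the estimated variance. With three parameters and 30 participants, neither effect is negligible.

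At stake are the primary p-value and confidence interval. The sentence in section 14.3 covers several estimators that give different p-values on the same data. If the form is not fixed before unblinding, the choice stays open after results are seen, and some of the permitted choices exceed the 0.05 level on which section 14.2 relies.

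**Working it through.** **Inputs.** From section 14.2: 15 per arm, type I error 0.05, SD 8.9, correlation 0.75, and 10% attrition (30 × 0.9 = 27 participants). From section 14.3: a model with intercept, arm and baseline BMI, hence 3 parameters and 30 − 3 = 27 residual degrees of freedom. A two-sided test is assumed; the documents do not state sidedness, but two-sided reproduces their power figure. Under section 14.4, "for the primary analysis we will use a last observation carried forward approach for participants on whom we do not have a final measurement", so the primary analysis may keep close to 30.

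**The plan's own figure.** Residual SD = 8.9 × √(1 − 0.75²) = 5.89. Standard error of the difference = 5.89 × √(2/15) = 2.15. Detectable difference = (1.96 + 0.84) × 2.15 = 6.02%, and power for 6% is 79.7%. With 13.5 per arm the detectable difference is 6.35%. Both agree with the stated 6% and 6.3%, and both use normal quantiles.

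**The estimators.** Let c be a participant's weight in the treatment estimate, e the residual and h the leverage. The variance of the treatment effect is then:
- HC0: Σ c²e²
- HC1: HC0 × n/(n − 3)
- HC2: Σ c²e²/(1 − h)
- HC3: Σ c²e²/(1 − h)²

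**A check by hand.** Average leverage is 3/30 = 0.10, so HC0 standard errors should be about √0.90 = 0.95 of the right size. The HC1 factor is √(30/27) = 1.054.

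**Simulation under no treatment effect.** 200,000 trials per row, normal baseline and errors, residual SD 5.89. The Monte Carlo standard error is about √(0.05 × 0.95/200,000) = 0.05 percentage points. Interval widths are mean 95% widths in percentage points of BMI change.

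| Split | Estimator | Type I, normal quantiles | Type I, t quantiles | Width, normal | Width, t |
|---|---|---|---|---|---|
| 15/15 | HC0 | 7.55% | 6.37% | 8.05 | 8.43 |
| 15/15 | HC1 | 6.19% | 5.13% | 8.49 | 8.89 |
| 15/15 | HC2 | 6.17% | 5.11% | 8.50 | 8.90 |
| 15/15 | HC3 | 4.94% | 4.02% | 8.98 | 9.40 |
| 15/15 | Least squares | 6.08% | 5.02% | 8.50 | 8.90 |
| 14/13 | HC0 | 7.88% | 6.51% | 8.44 | 8.89 |
| 14/13 | HC2 | 6.29% | 5.15% | 8.97 | 9.44 |
| 14/13 | HC3 | 4.96% | 3.96% | 9.54 | 10.05 |

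Least squares with t should give 5.0% here and does. The HC1 factor also checks: 8.05 × 1.054 = 8.48, against 8.49.

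For HC0 with normal quantiles at 15/15, coverage is 100 − 7.55 = 92.4%, and width relative to least squares with t is 8.05/8.90 = 0.904, about 10% too narrow. That splits into 8.05/8.50 = 0.947 from the variance bias, close to the 0.95 found by hand, and 8.50/8.90 = 0.955 from the quantile.

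**Other assumed distributions.** Type I error for HC0 with normal quantiles was 7.2% with heavy-tailed (t with 4 df) errors, 7.5% with a lognormal baseline and 7.8% with a 2:1 ratio of residual SDs between arms. With lognormal errors it was 6.2% to 6.6%. Separate runs of the 15/15 normal case gave 7.4% to 7.6%.

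**Power for a 6% difference.** At 15/15: HC2 with t 75.3%, least squares with t 75.3%, HC3 with t 71.5%. At 14/13: HC2 with t 70.1%, HC3 with t 65.6%. For 6.3% at 14/13, HC2 with t gives 74.3%.

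**The case against.** The strongest reply is that the plan has not chosen a bad method; it has left the method unnamed. A reader might infer from section 14.3 that the trial will run at about 8% type I error with 92% coverage. The documents do not support that. They mention neither HC0 nor normal quantiles, and a careful analyst could use HC2 with t and satisfy the sentence as written. The 8% figure is the upper end of a range, and it is lower with skewed errors. This part of the objection stands in full.

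A reader might also infer that t quantiles are indispensable. They are not: HC3 with normal quantiles gives 4.9% at 15/15. Nor do t quantiles rescue HC0, which stays at 6.4%.

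A third tempting step is to apply the same figures to all five secondary outcomes. Only the baseline-adjusted model with the distributions listed was examined. Ratio outcomes such as the c-peptide index were not simulated, and section 5.2 collects total daily insulin dose for participants on insulin, so that analysis may have a different sample size and distribution.

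Finally, this is a pilot whose sample size was set by feasibility. That lowers the stakes but does not remove them, because the plan states hypotheses, a significance threshold and a power claim.

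None of this argues for dropping robust variance. In a stress case the plan does not foresee (18/12, with twice the residual SD in the smaller arm), least squares with t gave 8.5%, against 6.0% for HC2 with t.

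**Conclusion.** The concern holds as a gap in specification with a measurable consequence. For the primary analysis at about 15 per arm under normal errors, type I error is about 7.6% to 8% for HC0 with normal quantiles, about 6.2% for HC1 or HC2 with normal quantiles, about 5.1% for HC1 or HC2 with t, and about 4% for HC3 with t. The 0.05 level in section 14.2 is therefore met only under some readings of section 14.3.

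The type I error figures do not depend on the residual SD, but they do depend on the assumed shapes of the baseline and error distributions, for which the documents give only an SD and a correlation. The power figures also depend on the residual SD of 5.89. The effect is on how the interval and p-value are read, not on the choice of 30 participants.

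**What to change.** Before unblinding, state in section 14.3 that confidence intervals and p-values for the primary and secondary baseline-adjusted models use the HC2 heteroscedasticity-consistent variance, with t quantiles on n minus the number of model parameters (27 degrees of freedom for the primary model with all 30 participants). HC3 with t is a more conservative option at about 4% type I error, but it costs 75.3 − 71.5 = 3.8 points of power for a 6% difference. HC2 is the better default. State also that the test is two-sided. The longitudinal analyses have repeated measurements per participant and need their own statement of variance form, which was not examined here.

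Restate the power in section 14.2: about 75% for a 6% difference with HC2 and t at 15 per arm (about 71% with HC3 and t), and about 74% for 6.3% at 14/13. The reduction is not a price of HC2, since least squares with t has the same 75.3%; the stated 80% rests on normal quantiles.

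The cost is one sentence, a software option and a revised power statement. No new data, participants or design changes are needed.
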